# Contemplative Neuroscience & Integrative Medicine Laboratory

- history of sustained loss of consciousness, major neurological or medical illness (including significant head trauma defined by loss of consciousness  $\geq 5$ -minutes duration), alcoholism or other substance abuse, significant learning disability, left-handedness, pregnancy,
- fMRI specific: claustrophobia, presence of a ferromagnetic object, presence of opiates and/or amphetamines through urine tests on day of scans.

## 4.0 Enrollment/Randomization

Pre-screening questionnaire using REDCap will be assessing eligibility criteria for the multiple diagnostic arms and methodologies in this study. Suicidal ideation is probed in the BDI-II (item 9) administered in the pre-screening questionnaire and in weekly assessments. Endorsement of any response other than a 0 (indicative of no suicidal ideation) will automatically prompt an email alert to the PI, the study coordinator, [name], JD, MSN, PMHNP-BC (psychiatric nurse practitioner who has 12+ years of experience diagnosing and treating people with a wide range of psychiatric disorders, including depression), and [name]., clinical psychologist at the Osher Center. Follow-up to assess risk and clarify an action plan for protecting the participant will occur within 24 hours and is detailed in the attached suicide safety plan.

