## Contemplative Neuroscience & Integrative Medicine Laboratory

- Deliberate awareness of routine activities and events such as: eating, weather, driving, walking, awareness of interpersonal communications

f) Daily home assignments including a minimum of 45 minutes per day of formal mindfulness practice and 5-15 minutes of informal practice, 6 days per week for the entire duration of the course

g) Individual and group dialogue and inquiry oriented around weekly home assignments including an exploration of hindrances to mindfulness and development and integration of mindfulness-based self-regulatory skills and capacities

h) Incorporation of exit assessment instruments and participant self-evaluation in Class 8

- Total in-class contact: 30+ hours
- Total home assignments: minimum of 42-48 hours
- Total group Orientation Session time: 2.5 hours

Mindfulness-based Cognitive Therapy (MBCT) (Appendix B). 8-week MBCT treatment protocol is standard as defined by Segal, Williams and Teasdale(Segal, Williams et al. 2013) with some minor modifications to address suicidality and presence of acute symptoms, i.e., introduction of crisis plans and cognitive components addressing suicidal cognitions and hopelessness. MBCT uses core meditation techniques (i.e., focused attention, open monitoring, body scan, breathing space, yoga) with a focus on mindful awareness as its core therapeutic ingredient and adds components of cognitive behavior therapy (CBT) (Segal, Williams et al. 2013).

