**Risk Minimization:** All members of the research team will be sensitive to the needs of participants by reminding them that they do not need to answer any questions that they would prefer not to answer, complete any tasks that they would prefer not to complete, or follow through with any procedure that they would rather decline. Study staff will use their clinical judgment to discontinue assessment if a participant appears upset.

Notably, suicidal ideation is probed in the BDI-II (item 9). Endorsement of any response other than a 0 (indicative of no suicidal ideation) will automatically prompt an email alert to the PI, the study coordinator, [name], JD, MSN, PMHNP-BC (psychiatric nurse practitioner who has 12+ years of experience diagnosing and treating people with a wide range of psychiatric disorders, including depression), and [name]., clinical psychologist at the Osher Center. Follow-up to assess risk and clarify an action plan for protecting the participant will occur within 24 hours and is detailed in the attached suicide safety plan.

**Activity:** Completion of an eight-week psychobehavioral intervention.

**Risk(s):** Risks associated with psychotherapy are minimal. Participants may experience discomfort while talking about their symptoms, emotions, experiences, or daily routines. They may experience clinical worsening as they attempt to make any recommended behavioral changes.

**Risk Minimization:** Intervention facilitators will be sensitive to the needs of participants and available for support by phone on a daily basis, if needed. Weekly, the study medical monitor ([name], JD, MSN, PMHNP-BC) will review participants' medication status and depressive and/or anxious symptom scores and ensure referral to appropriate care for those who show evidence of substantial worsening.

**Activity:** Administration of visual or auditory stimuli related to cognitive/emotional functions, including the use of words with negative affective valence, which may be emotionally-charged in content and relate to themes that patients with affective disorders often express. Control words will be affectively neutral and matched for word length, number of syllables, etc. with emotionally-laden words.

**Risk(s):** Some stimuli may be perceived as distressing by a given participant due to that participant's underlying perceptual or emotional impairment.

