## **7.0 Reporting of Adverse Events or Unanticipated Problems involving Risk to Participants or Others**

Participants could react adversely during the assessment and/or intervention procedures or symptoms could worsen during the course of the study (although this worsening may or may not be related to the treatment). Once weekly during the eight-week MBCT or MBSR intervention, participants will complete a brief medication questionnaire, the Beck Depression Inventory-II, and the Spielberger State-Trait Anxiety Inventory. The PI and study coordinator will examine weekly medication status and symptom scores with the appointed study medical monitor ([name], JD, MSN, PMHNP-BC) and note changes. If we see evidence of substantial worsening, at-risk participants will be removed from the study and appropriate safety measures will be taken. Dropout rates will be examined at least quarterly, depending on enrollment. If there are concerns about attrition, the research team will review information regarding each participant who withdrew and study procedures, and ensure adequate subject protection and data integrity.

Reporting of adverse events will occur as follows:

During the study, if patients become unstable, [name], the Psychiatric mental health nurse practitioner, will be monitoring clinical change and risk of suicidality.

Any serious adverse event (e.g., death, suicide attempt, hospitalization) will be reported by telephone within 24 hours to the IRB and the DSMB. A full written report of the event will be sent to these entities within 24 hours of the event's occurrence.

Any moderate adverse event (e.g., causing interference with usual activities or requiring treatment) and which appears definitely, probably, or possibly related to study participation will be reported to the IRB and DSMB in writing within seven working days. Any mild adverse event will be summarized in the IRB annual progress reports.

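### As written, a declined BDI-II item 9 does not trigger the suicidality alert or the 24-hour follow-up

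*Combined protocol and SAP*

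**What the plan says.** Section 4.0 (Enrollment/Randomization) names item 9 of the BDI-II as the probe for suicidal ideation, at pre-screening and in the weekly assessments. The rule is: "Endorsement of any response other than a 0 (indicative of no suicidal ideation) will automatically prompt an email alert". The alert goes to the PI, the study coordinator, a psychiatric nurse practitioner and a clinical psychologist. Risk is then to be assessed within 24 hours, by a process that "is detailed in the attached suicide safety plan". Section 6.0 (Risks) repeats the same rule.

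The Section 6.0 entry on self-report questions also describes how participants' privacy is protected. Staff do this by "reminding them that they do not need to answer any questions that they would prefer not to answer". The next paragraph restates the item 9 rule and does not exempt item 9 from that right.

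Section 3.0 makes absence of current suicidal ideation an eligibility criterion for every arm. Section 7.0 sets the weekly schedule: "Once weekly during the eight-week MBCT or MBSR intervention, participants will complete a brief medication questionnaire", together with the BDI-II and the State-Trait Anxiety Inventory. On review, it says: "The PI and study coordinator will examine weekly medication status and symptom scores with the appointed study medical monitor".

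**The concern.** An automated alert acts only on the condition it is given. Here the condition is a non-zero answer, and the protocol separately tells participants that they need not answer. Someone unwilling to disclose suicidal thoughts can therefore use a right that staff have pointed out and, on the written rule, produce no alert.

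The alert is the only route in the protocol with a stated deadline for assessing a participant's suicide risk. The other 24-hour limit, in Section 7.0, concerns reporting serious adverse events that have already happened. One arm is selected for a BDI-II score of 14 or more. At pre-screening the same item is the stated probe for an eligibility criterion, so a blank also leaves that criterion unsettled.

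**Working it through.** No arithmetic bears on the rule itself, so the check sets the relevant sections side by side.

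**Step 1: apply the written trigger (Sections 4.0 and 6.0) to each possible state of item 9.**

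| State of item 9 | Action stated |
|---|---|
| 0 | No alert |
| Any non-zero response | Email alert, then follow-up within 24 hours |
| Declined or blank | None stated |

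**Step 2: ask whether the third state can arise.** The Section 6.0 reminder sits under the activity of answering self-report questions about history and current health, which takes in the BDI-II. It is general and has no exception. The authors foresaw unanswered items elsewhere: Section 5.0 pro-rates PROMIS scores when items are skipped. No such rule is given for the BDI-II total or for the alert.

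**Step 3: ask whether another safeguard catches a blank.**

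- *Weekly score review (Sections 6.0 and 7.0).* It is unconditional, but it looks at medication and symptom scores and acts on marked deterioration. A missing item is not said to count.
- *Nurse-practitioner monitoring (Section 7.0).* The nurse practitioner "will be monitoring clinical change and risk of suicidality", but the sentence applies once a patient is unstable.
- *Instructor judgement (Section 8.0).* This appears as a criterion for terminating a participant.
- *Daily telephone support from facilitators (Section 6.0).* It is available when needed.
- *Crisis plans (Section 1.0).* The MBCT course includes "introduction of crisis plans and cognitive components addressing suicidal cognitions and hopelessness". The MBSR outline does not mention them; Appendix A was not available to check.

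None is tied to an unanswered item 9, and none has a deadline for assessing risk. Weekly review, instructor judgement, telephone support and crisis plans belong to the intervention period, so they offer little at pre-screening.

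**Step 4: scope.** Section 9.0 plans 42 participants in the Anxiety Arm, 26 in the Depression Arm and 30 in the high stress/chronic pain Arm: 42 + 26 + 30 = 98, if no one is counted in two arms. The 30 healthy paradigm-testing subjects are left out because they do not complete the full pre-screening questionnaire (Section 3.0). People who are pre-screened but never enrol are also covered by the rule; the documents do not give their number.

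**The case against.** The strongest reply is that the governing detail lies elsewhere. The suicide safety plan is the natural home for rules on declined answers, and the REDCap build holds the required-field and skip settings. Neither was available. A coded decline option might even count as a response other than 0. On this view the point is a query to the sponsor. That limit stands, and it is why checking those sources comes first. However, Section 4.0 cites the safety plan for how follow-up is done, without saying that it widens the trigger, and the protocol describes no decline option.

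Second, the right to decline is a general statement on voluntariness, while Section 7.0 expects participants to complete the BDI-II each week. It is true that no text shows a form being submitted without item 9. But the general wording permits it, and item 9 is named in the next paragraph without an exception.

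Third, reviewers could reasonably be expected to notice an incomplete BDI-II, and someone who has not answered the probe has not been shown to meet the eligibility criterion. Both are sensible practice, but neither is written down. A weekly review also need not reach the participant within 24 hours.

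Fourth, no frequency is known, and 98 is planned enrolment, not a count of people affected. This stands in full. So does the remark that this is a matter of safety procedure and form design: it does not affect endpoints, sample size or analysis.

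**Conclusion.** The concern holds as stated. On the written rule, a declined or blank item 9 leads to no alert and no 24-hour contact, and nothing else in the protocol says what to do. This is more than missing detail, because an automated trigger built exactly as described would stay silent for an answer the protocol allows.

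The size is one of scope only: up to 98 planned participants, assuming no overlap between arms, with weekly BDI-II under both MBCT and MBSR. No rate of declined items and no effect on scores is claimed. Confidence is medium, because the safety plan and the REDCap settings may already close the gap; it is not shown that a blank goes unhandled in practice. The point is worth acting on as a cheap safety improvement.

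**What to change.** 1. Check the suicide safety plan and the REDCap build. If either already treats an unanswered item 9 as a trigger, one clarifying sentence in the protocol is enough.
2. Otherwise, make item 9 a required field with an explicit option to decline, which keeps the right not to answer.
3. State in Sections 4.0 and 6.0 that choosing that option, or leaving the item blank, prompts the same alert and the same 24-hour contact as a non-zero answer. What happens at that contact stays with the safety plan.
4. At pre-screening, treat the suicidal-ideation criterion as unresolved until the answer has been clarified.

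The cost is one field and alert setting, one sentence in each of two sections, and a few extra contacts with people who merely skipped the item. Because declining would now prompt a contact, the clinicians who own the safety plan should agree the wording. The change does not deal with a weekly survey that is never submitted.

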## 5.0 Study Procedures

### BEHAVIORAL OBSERVATION

[figure not shown]

FIGURE 1. Inclusion criteria and allocation of research protocol. Pre-screening includes demographics and surveys specific for determining extent of anxiety (STAI), depression (BDI), and stress (PSS). Subjects with moderate levels of depression or anxiety will then have the choice to participate in EEG (cognitive go-nogo, emotional go-nogo, n-back, , and S-EAF tasks) and fMRI (fMRI-based emotional go-nogo task).

Anxious subjects will be recruited specifically for a dot-probe task with EEG protocol. Subjects who are interested in MBSR, have pain and report moderate levels of stress will take part in behavioral testing (emotional go-nogo). All subjects will have the opportunity to provide blood for inflammatory analyses. High anxiety and depression are anticipated to be reported by subjects enrolled in MBCT; whereas, high levels of pain and stress are anticipated to be reported by subjects enrolled in MBSR. RED color indicates symptoms of anxiety from screening, BLUE indicates depressive symptoms; ORANGE indicates pain symptoms; GREEN indicates Stress-related symptoms.

Respondent Burden Estimates (Behavioral Tasks/fMRI/EEG/Blood-based Markers)			
EEG: (Total: 137-180 min) Setup (25-30 min), Baseline (6 min) Cognitive Go-NoGo (15 min) Emotional Go-NoGo (30 min) N-Back (23 min) S-EAF (36 min) Dotprobe (25 min)	MRI: (Total: 57-62 min) Setup (10-15 min) Structural MPRAGE Scan (5 min) DWI/HARDI scan (6min) Baseline Rest (6 min) Emotional Go-NoGo (30 min)	Behavioral Testing: (Total: 35 min) Setup (3-5 min) Cognitive Go-NoGo (15 min) Emotional Go-NoGo (30 min)	Inflammatory Markers: (Total: 20 min) Setup (10-15 min) Blood draw (5 min)

#### Self-Report Measures (Pre/post-testing and follow-up)

**Patient Reported Outcomes Measurement Information System (PROMIS-29) ®:** A flexible set of tools designed to measure self - reported physical, mental and social health and wellbeing across seven PROMIS domains in 29 items: depression; anxiety; physical function; pain interference; fatigue; sleep disturbance; and ability to participate in social roles and activities. The seven domains cover the most relevant areas of self - reported health for the greatest majority of people with chronic illness. **Only the anxiety and pain interference domains will be** with each domain consisting of 4 questions ranked on a 5-point Likert Scale. There is also one 11-point rating scale for pain intensity. Response scores from the items that were answered (not including any screening question). Multiply this sum by the total number of items in the short form. Finally, divide by the number of items that were answered. For example, if a respondent answered 5 of 8 questions and answered all items with the second lowest response option (2), you would sum all responses (10), multiply by the number of items in the short form (8) and divide by the number of items that were answered (5). Here  $(10 \times 8) / 5 = 16$ . If the result is a fraction, round up to the nearest whole number. This is a pro-rated raw score which is then converted to a T-score. The T-score rescales the raw score into a standardized score with a mean of 50 and a standard deviation (SD) of 10.

**Five Facet Mindfulness Questionnaire (FFMQ; Baer et al., 2006) (7-10 min):** A 39-item assessment of trait mindfulness (encompassing observing, describing, acting with awareness, non-judging, and non-reactivity), which takes roughly 7-10 minutes to complete.

**Rumination Response Scale (RRS; Nolen-Hoeksema & Morrow, 1991) (5-10 min):** 22-item assessment that reliably assesses rumination and not confounded by depression. The 22 items of the RRS measure two aspects of rumination, brooding and reflective pondering. Items are rated on a four-point scale: 1-Almost Never, 2-Sometimes, 3-Often, 4-Almost always. The questionnaire provides scores for the following scales: Brooding, Reflection, and Depression.

**Behavioral Inhibition (BIS/BAS scale; (Carver and White 1994) (10 min):** The BIS/BAS Scale is a 24-item self-report questionnaire designed to measure two motivational systems: the behavioral inhibition system (BIS), which corresponds to motivation to avoid aversive outcomes, and the behavioral activation system (BAS), which corresponds to motivation to approach goal-oriented outcomes.

Participants respond to each item using a 4-point Likert scale: 1 (very true for me), 2 (somewhat true for me), 3 (somewhat false for me), and 4 (very false for me). The scale has four subscales that were derived via factor analysis. One subscale corresponds to the BIS. Seven items contribute to this score (e.g., "Criticism or scolding hurts me quite a bit"). The remaining three subscales correspond to three components of BAS. BAS Drive measures the motivation to follow one's goals. Four items contribute to this score (e.g., "When I want something I usually go all-out to get it"). BAS Reward Responsiveness measures the sensitivity to pleasant reinforcers in the environment. Four items contribute to this score (e.g., "It would excite me to win a contest"). BAS Fun Seeking measures the motivation to find novel rewards spontaneously. Five items contribute to this score (e.g., "I crave excitement and new sensations").

**Depression Anxiety Stress Scale (DASS) (10 min):** The Depression, Anxiety and Stress Scale - 21 Items (DASS-21) is a set of three self-report scales designed to measure the emotional states of depression, anxiety, and stress. Each of the three DASS-21 scales contains 7 items, divided into subscales with similar content. The depression scale assesses dysphoria, hopelessness, devaluation of life, self-deprecation, lack of interest / involvement, anhedonia and inertia. The anxiety scale assesses autonomic arousal, skeletal muscle effects, situational anxiety, and subjective experience of anxious affect. The stress scale is sensitive to levels of chronic non-specific arousal. It assesses difficulty relaxing, nervous arousal, and being easily upset / agitated, irritable / over-reactive and impatient. Scores for depression, anxiety and stress are calculated by summing the scores for the relevant items. The DASS may hold more promise for distinguishing between anxiety and depression, as well as between symptoms of physical arousal and symptoms of generalized anxiety (e.g., tension or agitation). The DASS-A will be used as the primary outcome measure of anxiety.

**Carol Ryff scales of psychological well-being (Ryff) (10 min):** Two 9-item scale for purpose in life and self-acceptance are included for testing well-being. Participants respond using a six-point format: strongly disagree (1), moderately disagree (2), slightly disagree (3), slightly agree (4), moderately agree (5), strongly agree (6). Responses to negatively scored items (-) are reversed in the final scoring procedures so that high scores indicate high self-ratings on the dimension assessed. Please note, there are no specific scores or cut-points for defining high or low well-being. Those distinctions are best derived from distributional information from the data collected. For example, high well-being (for short or long versions of the scales) could be defined as scores that are in the top 25% (quartile) of the distribution, whereas low well-being could be defined as scores that are in the bottom 25% (quartile) of the distribution.

**Patient Activation Measure Short Form (PAM-13; Hibbard, Mahoney, Stockard, & Tusler, 2005) (10 min):** The Patient Activation Measure is a 13-item scale designed to measure patients' beliefs, confidence, knowledge, and skills regarding health management. Items are rated on a four-point scale with an additional "not applicable" option: (1) Disagree Strongly, (2) Disagree, (3) Agree, (4) Agree Strongly.

**Pain Catastrophizing Scale (PCS; Sullivan, Bishop, Pivik, & Bitcher, 1995) (5 min):** The Pain Catastrophizing Scale is a 13-item scale designed to measure pain on three subscales: rumination, magnification, and helplessness. Items are rated on a five-point scale ranging from (0) Not at all to (4) All the time. A total

## Contemplative Neuroscience & Integrative Medicine Laboratory

PCS score is derived by summing all 13 items. Scores range from 0 to 52, with higher scores indicating greater catastrophizing.

### **Daily Survey**

**Home Meditation Practice** [daily during intervention]: Participants will be asked to record the frequency and duration of formal home practice sessions, which will take roughly 1-2 minutes to complete daily for eight weeks.

### **Weekly Survey**

**Treatment Regimen Check-In** [weekly during intervention, posttest visit]: Participants will be asked to report whether their depression and/or anxiety medication regimen has changed or if any new, additional treatments have been initiated within the past week, which will take roughly 1-3 minutes to complete once weekly for eight weeks.

**Beck Depression Inventory-II** (BDI-II; Beck et al., 1996) [initial screening, weekly during intervention, posttest visit]: A 21-item measure that evaluates key affective, cognitive, and neurovegetative symptoms of depression listed in the *Diagnostic and Statistical Manual of Mental Disorders—Fourth Edition* (DSM-IV; American Psychiatric Association, 1994) and takes roughly 5-10 minutes to complete.

**Spielberger State-Trait Anxiety Inventory** (STAI; Spielberger et al., 1983) [initial screening, weekly during intervention, posttest visit]: A 40-item inventory that measures presence and severity of current anxious symptoms (i.e., state anxiety) and a general propensity to be anxious (i.e., trait anxiety). It takes roughly 5-10 minutes to complete.

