### **3.0 Inclusion/Exclusion Criteria**

Eligibility Criteria for Pre-Study Paradigm Testing:

- Before commencing the research delineated in this protocol, we will collect EEG and fMRI data from 30 healthy subjects to test all of our experimental paradigms and make sure they are working properly.
- Flyers and ResearchMatch will be used to circulate information about the study to the Vanderbilt campus and surrounding community.
- The subjects must be between the ages of 18 and 55.
- The 30 subjects will not complete the full pre-screening questionnaire, but will receive a phone screen to make sure they can safely participate in the EEG and fMRI protocol.

Eligibility Criteria Across All Study Arms:

- At prescreen, must be currently registered for MBCT or MBSR; at posttest, must have attended five of eight sessions for “completion”.
- Must possess English language skills sufficient for providing informed consent, completing questionnaires, and understanding instructions
- Age range: 18-55

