## Contemplative Neuroscience & Integrative Medicine Laboratory

- If currently taking maintenance anti-depressant and/or anti-anxiety medication, must have a "stable" regimen as indexed by no medication or dosage changes within the past month
- No prior diagnosis of bipolar I, bipolar II, psychotic personality disorder, borderline personality disorder, and/or narcissistic personality disorder
- No current history ( $\leq 6$  months) of substance abuse/dependence
- No current history ( $\leq 6$  months) of regular meditation practice ( $>1$  session/week;  $>10$  min/session)
- No history of medical illness associated with possible changes in cerebral tissue or cerebrovasculature (e.g., stroke) or with neurologic abnormality (e.g., seizure disorder, cerebrovascular or neoplastic lesion, neurodegenerative disorder, or significant head trauma, defined by loss of consciousness of  $\geq 5$  minutes)
- No current suicidal ideation

*Depression Arm (consists of fMRI scan, EEG with behavior, and self-report measures at pre- and post-treatment testing)*

- Beck Depression Inventory-II (BDI-II) score  $\geq 14$  (an indicator of depressive symptoms of mild to high severity)
- No fMRI contraindications: pregnancy, claustrophobia, or presence of a ferromagnetic object, including orthodontic braces

*Anxiety Arm (consists of EEG with behavior, fMRI scan, self-report measures at pretest and posttest)*

- Diagnosed (via SCID-V Screener) with an anxiety disorder (i.e., generalized anxiety disorder, panic disorder, specific phobia)
- Score of  $\geq 40$  on the Trait subscale of the Spielberger State-Trait Anxiety Inventory (an indicator of anxious symptoms of moderate to high severity)

*Stress Arm*

- Moderate to high stress is necessary for inclusion on behavioral testing/self-report
- Scores on PSS pre-screen  $> 14$  would be considered moderate to high perceived stress.

*Blood Draws (consists of a 10-mL draw at pre-treatment baseline and post-treatment testing; optional for depression/anxiety arm participants)*

Eligibility Criteria:

- At least 110 pounds
- Generally healthy by self-report on day of collection (i.e., free of cold and flu symptoms on the day of collection, no infections within two weeks prior to collection, no known sickle cell disease)
- Including the study draw, blood donation for clinical or research purposes within the preceding eight weeks will not exceed 550 mL
- No more than one blood draw will have occurred during the preceding week

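### Does using BDI-II to select the Depression Arm, with no listed pretest BDI-II, bias a result the plan will report?

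*Combined protocol and SAP*

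**What the plan says.** - **Selection.** Section 3.0 Inclusion/Exclusion Criteria admits patients to the Depression Arm at BDI-II of 14 or more, described as "an indicator of depressive symptoms of mild to high severity". The Figure 1 legend in section 5.0 says that pre-screening contains "surveys specific for determining extent of anxiety (STAI), depression (BDI), and stress (PSS").
- **Schedule.** The Weekly Survey part of section 5.0 lists BDI-II as "initial screening, weekly during intervention, posttest visit]: A 21-item measure". Section 4.0 agrees: the scale is "administered in the pre-screening questionnaire and in weekly assessments". Section 7.0 says "Once weekly during the eight-week MBCT or MBSR intervention, participants will complete a brief medication questionnaire", followed by BDI-II and STAI. None of these places says whether the first weekly survey comes before or after session 1.
- **Pretest battery.** The Self-Report Measures list in section 5.0, headed as pre/post testing and follow-up, includes DASS-21 with its depression scale, but not BDI-II. Section 3.0 promises the Depression Arm "self-report measures at pre- and post-treatment testing" without naming the scales.
- **No untreated group.** At prescreen every patient "must be currently registered for MBCT or MBSR".
- **Analysis.** Section 9.0 covers P1 ERP, fMRI and go/no-go outcomes. The only symptom scale named as a primary outcome is DASS-A, for anxiety (Self-Report Measures).

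**The concern.** Patients who pass a cutoff on a noisy scale have, on average, screening scores above their usual level. Their next score tends to be lower even if nothing has changed. If the selecting score also serves as the baseline, this drop is counted as improvement, and without an untreated group it cannot be separated from a treatment effect.

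The schedule seems to invite this. The screening BDI-II is the one score certain to precede treatment, and the first weekly score may follow session 1. Section 6.0 expects the work to clarify how the interventions reduce symptoms, and Aim 6 speaks of clinical outcomes, so a BDI-II change is an easy result to report. A drop of a point or so that is pure artefact could then be read as benefit. STAI-Trait has the same schedule and selects the Anxiety Arm at 40 or more, so the same question arises there.

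**Working it through.** The plan gives no figure for BDI-II change, so there is none to reproduce. The check has two parts: how large the artefact could be, and whether it reaches anything planned.

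**1. Size if the screening score were the baseline**

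Inputs from the plan: cutoff 14 (section 3.0) and n = 26 (section 9.0). The source mean, SD and correlation are not in the documents and are assumed: mean 18, 22 or 25; SD 10; screening-to-posttest correlation r of 0.90 or 0.75. The higher means reflect the Figure 1 legend: "High anxiety and depression are anticipated to be reported by subjects enrolled in MBCT".

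- Selection differential = SD × φ(a) / (1 − Φ(a)), with a = (14 − mean)/10
- Expected fall with no true change = differential × (1 − r)

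| Source mean | a | Differential | Fall, r = 0.90 | Fall, r = 0.75 | Significant, r = 0.90 | Significant, r = 0.75 |
|---|---|---|---|---|---|---|
| 18 | −0.4 | 5.62 | 0.56 | 1.40 | 9.4% | 17.2% |
| 22 | −0.8 | 3.68 | 0.37 | 0.92 | 6.9% | 10.1% |
| 25 | −1.1 | 2.52 | 0.25 | 0.63 | 5.8% | 7.3% |

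The last two columns come from 60,000 simulated trials of 26 patients with no true change, tested by a two-sided 5% paired t-test. The SD of change is about 4.4 at r = 0.90 and 6.8 to 6.9 at r = 0.75. The artefact is therefore 0.29 to 1.05 standard errors.

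These figures are not bounds. A separate calculation used cutoff 13.5 (for integer scores), means of 10 to 22, SDs of 8 to 12 and r of 0.6 to 0.9. It gave falls of 0.2 to 4.8 points. Its false-positive rates for r from 0.9 down to 0.6 were 9% to 24% at mean 18, SD 10, and 14% to 44% at mean 14, SD 10.

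**2. Size with a baseline that does not select**

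Artefact = differential × (r between screening and baseline − r between screening and posttest).

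- Equal correlations: artefact 0, rejection 5.0% to 5.1%.
- Correlations 0.95 then 0.90, mean 18: 5.62 × 0.05 = 0.28 points, rejection 7.3%.
- Correlations 0.85 then 0.75, mean 18: 5.62 × 0.10 = 0.56 points, rejection 7.9%.
- Correlations 0.95 then 0.90, mean 25: 2.52 × 0.05 = 0.13 points, rejection 5.5%.

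Where the correlation falls in this way, moving the baseline removes 0.13 to 1.1 points. The observed fall would be smaller on average but not in every trial: by normal approximation, in about 58% (mean 25, r between screening and baseline 0.95) to 82% (mean 18, r 0.80).

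**3. Does it reach a planned result?**

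- Depression Arm: the planned analysis is a repeated-measures ANCOVA of pre- and post-treatment fMRI data. BDI-II is not its outcome.
- Anxiety Arm: the power analysis concerns P1 amplitude, and the primary anxiety measure is DASS-A, taken before and after treatment and not used to select. For STAI-Trait (cutoff 40, SD 10, means 45 to 55, r of 0.90 and 0.75) the same formula gives 0.14 to 1.27 points, again for an analysis that is not planned.
- Stress arm: the power analysis concerns the go/no-go task.
- Stated uses of BDI-II: eligibility (3.0), the suicidality alert (4.0 and 6.0) and weekly symptom review (6.0 and 7.0). None depends on an estimate of mean change from screening.
- Non-response: section 8.0 assigns this label to patients terminated for worsening symptoms. It sets no BDI-II change threshold and so needs no BDI-II baseline.

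**The case for a change.** The strongest argument for acting is that the depression side has no named symptom outcome or baseline, and that the default pre-treatment BDI-II score is the biased one. A pre-treatment score that was never taken cannot be recovered later. The remedy would be about one sentence, and fixing the first weekly survey before session 1 would add no questionnaire.

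Much of this stands. The schedule is read correctly, the direction of the bias is certain, and an author who reported BDI-II change from screening would overstate it on average.

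It does not show that the plan as written goes wrong. The passage in section 6.0 is risk-benefit text about mechanisms and promises no estimate of depressive change. Nor is the study left without a usable baseline: DASS-21 depression is collected before treatment and does not select patients. It may carry some regression through its correlation with BDI-II, but less directly. The weekly BDI-II scores do not select either, and section 3.0 leaves room for a pretest BDI-II because it does not name its scales.

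The gain would also be limited. Without an untreated group, natural recovery and any slow regression stay in every pre-post difference, so no choice of baseline turns it into a treatment effect.

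**Conclusion.** The concern describes a real gap in detail but not a fault that needs a change to the plan. Following the plan as written produces no biased planned result, because no BDI-II change, response definition or screening-score baseline is specified.

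The 0.25 to 1.4 points and 6% to 17% false-positive rate belong to a hypothetical analysis. They rest wholly on an assumed source mean, SD and correlation, and a lower mean or correlation would raise them.

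An analyst who later chose to describe depressive change in this exploratory pilot would be expected to use DASS-21 depression or a BDI-II score that did not select the patients. The cutoff of 14 should not be re-applied to that score, and the result should be called uncontrolled change. The data for this are already being collected, although a first weekly score taken after session 1 would be a less clean baseline.
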